10.3. Outcomes related to biomarkers of mother-infant dyad at day 40-42 and 56+

- **Maternal anemia**, categorized as mild: Hb 11.0-11.9 g/dl, moderate: Hb 8.0-10.9 g/dl, and severe: Hb <8.0 g/dl. (5)
- **Maternal iron deficiency**, define by Ferritin <15 ng/mL (6) and (separately) Soluble transferrin receptor (sTfR) (IQR will be calculated)
- **Infant anemia**, categorized as mild: Hb -11.0-11.9 g/L, moderate: Hb 7.0-10.9 g/dl, and severe: Hb < 7.0 g/dl. (7)

- **Infant iron deficiency**, define by Ferritin <12ng/mL (6) and (separately) Soluble transferrin receptor (sTfR) (IQR will be calculated)
- **Maternal C-reactive protein (CRP) (mg/l)**, IQR will be calculated
- **Maternal alpha1-acid glycoprotein (AGP)**, IQR will be calculated
- Specific hypothesis driven analysis pertaining to breastmilk analysis – refer to plan of analysis developed with IMiC team at [name] Lab
- Specific hypothesis driven analysis pertaining to stool biomarker analysis – refer to plan of analysis developed with team at Stanford university.

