6.11. Laboratory sampling for study purpose only

- a) Breast milk samples on 50 randomly selected women from each arm will be collected for future assessment of micronutrients, macronutrients and microbiome. Aseptic hand expression technique will be followed for collection of breast milk for microbiome analysis (for Biobank for further analysis in future)
- b) Stool specimens will be collected from the same 50 randomly selected LWs and their infants from each arm for TaqMan Array Card (TAC) and Myeloperoxidase (MPO) using metagenomics approach (for Biobank for further analysis in future)
- c) Blood specimen will also be collected from the same 50 randomly selected LWs for the purpose of checking hemoglobin levels, serum ferritin, transferrin receptor and acute phase proteins such as AGP and CRP and for Biobank for further analysis in future for proteomics.
- d) Infant anemia, hemoglobin, serum ferritin, transferrin receptor and acute phase proteins such as AGP and CRP and for Biobank for further analysis in future for proteomics (for all enrolled subjects upon consent from parents).

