This is a community-based, open-label, multiarm randomized controlled trial that will include parallel group assignments with a 1:1:1 allocation ratio in low-income squatter settlements in urban Karachi, Pakistan. The women in the control group (control arm) will receive standard counseling only, whereas the lactating women in the first intervention group (intervention arm 1) will receive two sachets of balanced energy-protein (BEP) supplementation per day from enrollment until the infant reaches six months of age. The lactating women in the second intervention group (intervention arm 2) will receive the same BEP supplementation as those in intervention arm 1 while their babies will also receive a single stat dose (20 mg/kg orally) of Azithromycin at 42 days.

2. Objectives

The primary objective is to compare the efficacy of fortified, balanced energy-protein (BEP) supplements being consumed by lactating women for 6 months (intervention arm 1) with or without a single prophylactic dose of oral azithromycin to the infant at 42 days of age (intervention arm 2) with that of standard exclusive breastfeeding and nutritional counseling alone (control arm) in improving length velocity among infants at 6 months (outcome). The secondary outcome is to compare the impact of the interventions on weight (or growth) velocity, Z-scores, other anthropometry measures of infants, maternal weight changes, breast milk quality, gut microbiota, and key micronutrient levels in both the mother and infant.

3. Study setting and study population

The trial is being conducted in the peri-urban communities of Karachi, Pakistan. The study population includes only lactating women of reproductive ages who have recently delivered and their infants. Lactating women between 13 and 49 years of age and their newborns are the study population.

4. Primary hypothesis

Length velocity at 6 months of infant's age

H_a = Mean difference in length velocity of $>0.12\text{cm/month}$ to look at comparisons between multiple arms

H_o = Mean difference in length velocity of $\leq 0.12\text{cm/month}$ to look at comparisons between multiple arms

5. Secondary hypothesis

Growth velocity at 6 months of infant's age

H_a = Mean difference in growth velocity of $>0.4\text{ gram/kg/day}$ to look at comparisons between multiple arms

H_o = Mean difference in growth velocity of $\leq 0.4\text{ gram/kg/day}$ to look at comparisons between multiple arms

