The primary analysis will be by intention-to-treat (ITT) perform for those who had anthropometry at 6 months. All analyses will be done using Stata software version 16. The WHO 2009 Child Growth Standards will be used for age-sex standardization of child length, weight, head circumferences, MUAC and weight-for-height. Descriptive analysis of each arm will be conducted, and percentages or continuous data with SD will be reported.

The baseline characteristics will be assessed by arm. Outcomes of mean length velocity, growth velocity, weight gain, z scores and change in z score from 0-6 month will be compared using one way analysis of variance (ANOVA). Tukey's test will be used for multiple comparisons. As determined *a priori* the analysis will be adjusted for the birth weight and length of infant, maternal MUAC at enrollment, maternal age, gravida, maternal body mass index and gender of child using general linear model (GLM). Mixed model analysis will be used to compare change in outcome per month in the intervention arm compared to the control arm. Using repeated measures ANOVA, the analysis will report beta coefficients and 95% CI. The coefficients represents the rate of change in outcome per month. For covariate adjustment, an unadjusted and stepwise adjusted model will be run. Trajectories will be plotted for mean length and weight by age for each arm, and monthly z scores were also be plotted.

13. Potential sub-group analysis

The following variables will be considered for sub-group analysis for primary and secondary outcomes:

1. Birth weight i.e. <2500 gm and => 2500 gm
2. Maternal MUAC at enrolment i.e. < 21.0 cm and =>21.0 cm
3. Maternal age i.e. <30 years and => 30 years
4. Gravidity i.e. <3 and =>3
5. Maternal BMI i.e. <18.5 kg/m² and =>18.5 kg/m²
6. Gender of child

14. Missing Data

We will treat missing data as it is, no imputation will be applied. We discussed that due to growth flattering during this age, imputation maybe unreliable.

15. Interim analysis

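### SAP 10.3 defines maternal haemoglobin and ferritin only by cut-offs, in 50 women per arm, and plans no comparison of the measured levels

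*SAP*

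**What the plan says.** - **Objective.** SAP 2 lists among its secondary comparisons "key micronutrient levels in both the mother and infant".
- **Sampling.** Protocol 6.11 takes breast milk from a random subsample: "Breast milk samples on 50 randomly selected women from each arm will be collected". Maternal blood comes from the same women: "Blood specimen will also be collected from the same 50 randomly selected LWs for the purpose of checking hemoglobin levels, serum ferritin".
- **Outcome definitions.** SAP 10.3 defines maternal anaemia as "categorized as mild: Hb 11.0-11.9 g/dl, moderate: Hb 8.0-10.9 g/dl, and severe: Hb <8.0 g/dl". With no anaemia as the remaining class, this gives four ordered classes. Maternal iron deficiency is a two-class outcome: "define by Ferritin <15 ng/mL". Soluble transferrin receptor (sTfR), CRP and AGP stay on their own scale, with the note "IQR will be calculated".
- **Analysis.** In SAP 12 the ANOVA covers length velocity, growth velocity, weight gain and z-scores: "z scores and change in z score from 0-6 month will be compared using one way analysis of variance (ANOVA". No biomarker is named there, and the Table 3 shell for the 6-month results has no haemoglobin or ferritin row.
- **Contrast within the SAP.** SAP 10.2 keeps LAZ, WAZ and WLZ as continuous outcomes and lists stunting, wasting and underweight beside them.

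**The concern.** The objective speaks of levels, but the two maternal measures most directly tied to iron status appear as outcomes only after cutting. A threshold counts a woman only if the intervention moves her across it; movement elsewhere on the scale is lost. With 50 women per arm there is little information to spare. The supplement contains iron (Protocol 6.4.1, Table 2), so an effect on maternal iron status is plausible. A real shift could be reported as no difference in anaemia or iron deficiency when the measured values would have shown it.

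**Working it through.** **The plan's own power figure.** Protocol 11 gives 274 per arm, 319 after 14% dropout, and power 0.801 for length velocity (difference 0.12, SD 0.5, one-sided alpha 0.025). A one-sided t test with 274 per arm and a standardised difference of 0.12/0.5 = 0.24 gives 0.801, and 274/0.86 = 319. These figures reproduce. No power or detectable difference is stated for any biomarker.

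**Inputs.** n = 50 per arm (Protocol 6.11); cuts at 8, 11 and 12 g/dl for haemoglobin and 15 ng/mL for ferritin (SAP 10.3). Assumed: two-sided alpha 0.05 (the same critical value as one-sided 0.025), approximately normal values (ferritin after log transformation), the same shift for every woman, no lost samples, and one pair of arms at a time.

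**Step 1, measured scale.** A two-sample t test with 50 per arm reaches 80% power at 0.566 SD. The normal approximation, (1.960 + 0.842) × √(2/50), gives 0.560.

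**Step 2, yes/no cut.** If a proportion c of controls lies below the cut, the treated proportion is t = Φ(Φ⁻¹(c) − 0.566). With p̄ = (c + t)/2, power is

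Φ{ [c − t − 1.96√(2p̄(1 − p̄)/50)] / √([c(1 − c) + t(1 − t)]/50) }.

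At c = 0.30: t = Φ(−0.524 − 0.566) = 0.138 and c − t = 0.162. The null standard error is 0.0827, and 1.96 × 0.0827 = 0.162, so power is Φ(0.00) = 50%.

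| Control prevalence | Treated prevalence | Power |
|---|---|---|
| 5% | 1% | 18% |
| 10% | 3% | 27% |
| 20% | 8% | 41% |
| 30% | 14% | 50% |
| 50% | 29% | 60% |
| 60% | 38% | 61% |
| 70% | 48% | 60% |

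The maximum is about 61%, where the cut lies near the median of the two arms combined. The large-sample value agrees: relative efficiency there is 2/π = 0.637, and Φ(2.802 × √0.637 − 1.960) = 0.608. The ceiling moves little with alpha: 57% at 0.0167 two-sided, 59% at 0.025 two-sided, 63% at 0.05 one-sided.

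**Step 3, four haemoglobin classes analysed as ordered.** Relative efficiency is Σ(φᵢ − φᵢ₋₁)²/pᵢ, where pᵢ are the class probabilities and φᵢ the normal density at the cuts, evaluated midway between the two arms. Power is Φ(2.802 × √efficiency − 1.960).

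Example, control mean 12.5 g/dl and SD 1.2: the midpoint is 12.5 + 0.283 × 1.2 = 12.84. The class probabilities are about 0.000 (severe), 0.063 (moderate), 0.179 (mild) and 0.758 (none), and the densities at 8, 11 and 12 g/dl are 0.000, 0.123 and 0.312. Efficiency is 0.123²/0.063 + 0.189²/0.179 + 0.312²/0.758 ≈ 0.57, and power is 56%.

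| Assumed control mean (g/dl) | Power, SD 1.2 to 1.8 |
|---|---|
| 10.5 | 69% to 72% |
| 11.0 | 71% |
| 11.5 | 69% to 70% |
| 12.0 | 65% |
| 12.5 | 56% to 60% |
| 13.0 | 44% to 53% |

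A simulated tie-corrected Wilcoxon test on the four classes (6,000 runs per setting) agreed to within about two points at means of 10.5 to 12.5 (54% to 72%), against 79% to 81% for the t test on the measured values.

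**The case against.** The strongest reply is that SAP 10.3 is a list of outcome definitions, not of tests. No between-arm test is named for the anaemia classes or for ferritin, so any power figure belongs to a test the reader supplies. That stands, and the figures are conditional for this reason. It does not remove the point: the definitions already take haemoglobin and ferritin off their measured scale, and nothing elsewhere restores it.

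A reader might apply the 61% ceiling to the haemoglobin classes as well. The text does not support that. The definition yields four ordered classes, and an ordered analysis usually keeps more power than a single cut. The ceiling belongs to ferritin below 15 ng/mL and to any anaemia as yes/no.

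Nor is the iron information wholly dichotomised: sTfR stays on its own scale in the same bullet as ferritin. An IQR is a summary rather than a comparison, but the measure is kept. The maternal blood subsample is also not the smallest in the plan, since milk and stool come from the same 50 women per arm.

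The cut-offs come from cited guidance, and prevalence is easy to use in public health policy. That supports reporting the classes; it does not require the randomised comparison to rest on them.

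Finally, Protocol 7.2 places these measures among other pre-specified outcomes, without a hypothesis or power target, and the Protocol 7.3 table labels the maternal samples as for the biobank. This bears on severity, and it stands.

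**Conclusion.** The point holds, as a minor one. Maternal haemoglobin and ferritin are defined only by cut-offs although the objective concerns levels, and the SAP specifies no comparison of the measured values. For a difference with 80% power on the measured scale, a yes/no outcome loses at least about 19 percentage points (80% to 61%), and far more if the condition is uncommon. Ordered haemoglobin classes lose roughly 8 to 24 points (80% to between 72% and 56%) at assumed control means of 10.5 to 12.5 g/dl, and more at 13.

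These sizes depend on approximate normality or log-normality, an equal shift, and prevalences, means and SDs that the documents do not give. If the effect were concentrated in women below the cut, the loss could differ.

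Two wider inferences are not supported. The figures do not carry over to infants, because Protocol 6.11 plans infant blood for all enrolled infants whose parents consent, not for 50 per arm. Nor does anything here touch the primary analysis, the growth outcomes or the trial's sample size.

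**What to change.** In SAP 10.3, state the between-arm comparison for maternal haemoglobin as a mean difference in g/dl, and for maternal ferritin as a geometric mean ratio from log-transformed values, each with a 95% CI. Keep the anaemia classes and the proportion with ferritin below 15 ng/mL as descriptive summaries by arm. This follows the pattern SAP 10.2 already uses for z-scores and stunting, wasting and underweight. Infant haemoglobin and ferritin may be put on the same scales for consistency, but the power figures above are not an argument for that.

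The cost is a few sentences in the SAP and a few lines of code, with no new samples or visits. A mean difference is less directly clinical than a prevalence, but the prevalence is still reported beside it.

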7.3. Trial procedures for outcome assessment

Assessments/ Specimen	Arm	At enrolment	On each visit till age of 6 months	Monthly till age of 6 months	At 40-42 day of infants age (Before AZM dose)	At 56 day of infants age	At the age of 6 months (study endpoint)
Assessments at field							
Afzaish Sachet distribution and Compliance	B and C	✓	✓				
Azithromycin	C				✓ At 42 days		
Vital status	A, B, C	✓	✓				
Standard nutrition and health promotion counseling	A, B, C	✓	✓				
Infant anthropometry	A, B, C	✓		✓			✓
Maternal anthropometry	A, B, C	✓		✓			✓
24 hours Food Recall	A, B, C	✓		✓			✓
Lab investigations for study purpose (all Infants, where family is agree)							
Hemoglobin	A, B, C				✓	✓	
Serum Ferritin	A, B, C				✓	✓	
Transferrin receptors	A, B, C				✓	✓	
AGP	A, B, C				✓	✓	
CRP	A, B, C				✓	✓	
Proteomics (Biobank)					✓	✓	
Stool specimens (50 infants only)	A, B, C				✓	✓	
Lab investigations for Bio bank purpose only (50 LWs only)							
Breast milk	A, B, C				✓	✓	
Stool specimens	A, B, C				✓	✓	
Hemoglobin	A, B, C				✓	✓	
Serum Ferritin	A, B, C				✓	✓	
Transferrin receptors	A, B, C				✓	✓	
AGP	A, B, C				✓	✓	
CRP	A, B, C				✓	✓	
Proteomics (Biobank)	A, B, C				✓	✓	

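### Infant haemoglobin is defined only by anaemia classes, with a mild band printed in g/L and the mothers' 12.0 g/dl ceiling unjustified for age 6 to 8 weeks; no comparison of mean haemoglobin is planned

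*SAP*

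**What the plan says.** SAP 10.3 sets the infant anaemia outcome as "categorized as mild: Hb -11.0-11.9 g/L, moderate: Hb 7.0-10.9 g/dl, and severe: Hb < 7.0 g/dl" and cites a national nutrition survey for it. The maternal outcome in the same list is "categorized as mild: Hb 11.0-11.9 g/dl, moderate: Hb 8.0-10.9 g/dl, and severe: Hb <8.0 g/dl", with a WHO haemoglobin document as its source. The section title is "Outcomes related to biomarkers of mother-infant dyad at day 40-42 and 56", followed by a plus sign, so the second time point has no upper age limit.

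The table in Protocol 7.3 marks infant haemoglobin at two visits only: "At 40-42 day of infants age (Before AZM dose"), and day 56. There is no sample at 6 months. Protocol 6.11 plans infant blood "for all enrolled subjects upon consent from parents". Protocol 7.2 lists infant haemoglobin among the other pre-specified outcomes, without a cut-off.

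SAP 2 counts "key micronutrient levels in both the mother and infant" among the secondary aims. Infant iron deficiency is a separate item in SAP 10.3: "define by Ferritin <12ng/mL (6) and (separately) Soluble transferrin receptor (sTfR").

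On analysis, SAP 12 names length and growth velocity, weight gain and z scores for ANOVA, and no biomarker. SAP 10.3 promises an IQR for sTfR, CRP and AGP, but only classes for haemoglobin. The outcome table shell (Table 3) has no haemoglobin row.

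**The concern.** Three things come together in one line of the SAP.

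- **The unit.** The mild band is in g/L, while the other two bands are in g/dl. A programmer who follows the text literally cannot produce a usable grading.
- **The ceiling.** With the unit read as g/dl, an infant of 6 or 8 weeks is called anaemic below the same 12.0 g/dl as the mother. The SAP does not say why that limit suits this age.
- **The form of the outcome.** Haemoglobin is measured as a number in every infant whose parents agree, yet the only outcome derived from it is a class. If most infants fall below the ceiling, the any-anaemia proportion has little room to move, and much of the information in the blood samples is lost.

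At stake are the readability and sensitivity of one secondary biomarker outcome. A high reported prevalence could also be read as disease when it partly reflects the choice of cut-off.

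**Working it through.** There is no plan figure to reproduce: the documents state no expected prevalence, sample size or power for infant anaemia.

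**1. Unit.** g/L divided by 10 gives g/dl, so 11.0/10 = 1.10 and 11.9/10 = 1.19 g/dl. Both are below 7.0 g/dl, which is the severe band of the same line. Values of 11.0-11.9 g/dl are left without a grade. Reading the band as g/dl makes the grades contiguous (below 7.0, 7.0-10.9, 11.0-11.9), with any anaemia meaning below 12.0 g/dl. The hyphen before 11.0 is also stray, though it may come from the text conversion.

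**2. Infant and maternal limits side by side (infant mild band read as g/dl).**

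| | Infant | Mother |
|---|---|---|
| Mild | 11.0-11.9 | 11.0-11.9 |
| Moderate | 7.0-10.9 | 8.0-10.9 |
| Severe | below 7.0 | below 8.0 |
| Source cited | national survey | WHO document |

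The mild band and the 12.0 ceiling are shared. The moderate/severe limit and the source are not.

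**3. Share classed anaemic.** Mean μ and SD σ of infant haemoglobin at 6 to 8 weeks are not in the documents, so both are assumed. With a normal distribution, the share below 12.0 is Φ((12.0 − μ)/σ).

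- μ = 10.5, σ = 1.0: Φ(1.50) = 0.93
- μ = 11.5, σ = 1.2: Φ(0.42) = 0.66
- For μ of 10.5-11.5 and σ of 1.0-1.2 the range is therefore 66-93%.
- For σ of 1.0-1.5: 50% at μ = 12.0, 31-37% at 12.5 and 16-25% at 13.0.

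More than half are classed anaemic exactly when μ is below 12.0.

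**4. Power lost by using the class.** Assumptions: 274 infants per arm (the protocol's evaluable number for length velocity, taking every one of them as sampled), a shift of 0.3 g/dl, σ = 1.2, one pairwise comparison, two-sided 0.05.

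Continuous haemoglobin: SE = 1.2 × √(2/274) = 0.1025. Power = Φ(0.3/0.1025 − 1.96) = Φ(0.97) = 0.83, whatever the mean.

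Proportion below 12.0: power = Φ((|p1 − p2| − 1.96 × SE0)/SE1), with SE0 from the pooled proportion and SE1 from the separate ones. At μ = 10.5, p1 = Φ(1.25) = 0.894 and p2 = Φ(1.00) = 0.841, so the difference is 0.0530. SE0 = 0.0289 and SE1 = 0.0288. Power = Φ((0.0530 − 0.0567)/0.0288) = Φ(−0.13) = 0.45.

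| Assumed mean | Below 12.0 | Power, below 12.0 | Power, below 11.0 | Power, continuous |
|---|---|---|---|---|
| 10.0 | 95.2% to 92.2% | 0.31 | 0.56 | 0.83 |
| 10.5 | 89.4% to 84.1% | 0.45 | 0.63 | 0.83 |
| 11.0 | 79.8% to 72.0% | 0.56 | 0.64 | 0.83 |
| 11.5 | 66.2% to 56.6% | 0.63 | 0.60 | 0.83 |
| 12.0 | 50.0% to 40.1% | 0.64 | 0.50 | 0.83 |

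With σ = 1.0 the continuous power is 0.94. Over σ of 1.0-1.2 and means of 10.0-12.0, the 12.0 cut gives 0.29-0.80 against 0.83-0.94. For a 0.5 g/dl shift at σ = 1.2, the 12.0 cut gives 0.72, 0.88, 0.95 and 0.97 at means of 10.0, 10.5, 11.0 and 11.5, with continuous power close to 1.

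**The case against.** The strongest reply is that the central worry depends on facts outside the documents. A reader might infer that haemoglobin is naturally low at this age and that most healthy infants would be called anaemic. Neither document gives an infant haemoglobin range or an age-specific limit, and the survey cited for the bands is not available here. The inference is therefore conditional: it holds if the mean is below 12.0 g/dl and fails if it is above. This part of the reply stands.

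A reader might also infer that the outcome cannot show an effect on infant iron status. The documents do not support that. Iron deficiency has its own outcomes, ferritin and sTfR. The class proportions still respond to a shift, as the power figures show; they only respond less. Any excess caused by age would also affect all randomised arms alike, so the comparison between arms is not biased.

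Nor are the infants graded on the mothers' whole scale, since the moderate/severe limit and the source differ.

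Finally, the SAP writes no test of anaemia proportions by arm, and the protocol's wording does not confine reporting to classes. That is true, but it does not help the plan. A pre-specified outcome then has a class definition that cannot be programmed as printed and no stated comparison at all. Comparing moderate or worse (below 11.0) does not recover the loss either: its power is 0.50-0.64 in the table, against 0.83.

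**Conclusion.** The concern holds in a limited form. Three parts rest on the text alone: the unit error, the mild band and 12.0 g/dl ceiling shared with the mothers without an age-specific reason, and the absence of any planned comparison of haemoglobin as a measured value.

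The size of the consequence rests on assumptions. If mean haemoglobin at 6 to 8 weeks is below 12.0 g/dl, more than half of infants are classed anaemic. For a 0.3 g/dl shift the any-anaemia proportion then has clearly less power than mean haemoglobin. The 274 per arm is an upper figure for this purpose, since infant blood depends on parental consent; fewer samples would lower both powers. The continuous comparison is the more powerful at every mean and SD tried.

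This is a loss of sensitivity in a secondary biomarker outcome. The primary endpoint and the sample size are untouched.

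**What to change.** In SAP 10.3:

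1. Change g/L to g/dl in the infant mild band and remove the stray hyphen before 11.0.
2. Make the between-arm difference in mean infant haemoglobin (g/dl) at the day 56 visit, adjusted for age in days at sampling, the infant haemoglobin comparison. The age term is needed because the second time point is open-ended.
3. Do not treat the day 40-42 value as a baseline in comparisons with Arm A. Supplementation starts at enrolment (Protocol 6.9), so that value may already carry an effect of the intervention.
4. Keep the three classes as descriptive and label them as not age-specific, unless a justification for this age can be cited.
5. Add a row for mean infant haemoglobin to the results table shells.

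The cost is SAP wording and one linear model. Samples, assays and visits stay the same. The small downside is that readers know a prevalence better than a mean difference; keeping the descriptive classes meets that.

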(10) However, the treatment may have unintended consequences including possible adverse effects or resistance to antibiotics, but so far no data suggests resistance to a single oral prophylactic dose of AZM. (26) Furthermore, the mechanism of action of AZM is multidirectional and it plays a vital role in reducing inflammation because of its anti-inflammatory properties. (27, 28) Oral administration of AZM has also been found to improve the diversity of gut flora, improve immunity (29) and prevent the risk of infection among children. However, these theories have not been proven yet and further evidence to support prophylactic use of AZM among infants to promote infant growth is needed through large trials. Also, evidence from the combined effect of nutrition supplementation to lactating woman and prophylactic dose of AZM to infants is not yet available to see the overall impact on infants' growth outcomes.

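### Iron deficiency is defined from ferritin uncorrected for inflammation, so the infant day-56 comparisons with the azithromycin arm could show a spurious excess of deficiency

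*SAP*

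**What the plan says.** SAP 10.3 defines iron deficiency by fixed ferritin cut-offs. For infants it reads "define by Ferritin <12ng/mL (6) and (separately) Soluble transferrin receptor (sTfR) (IQR will be calculated", and for mothers "define by Ferritin <15 ng/mL (6) and (separately) Soluble transferrin receptor (sTfR) (IQR will be calculated". The same list includes maternal "C-reactive protein (CRP) (mg/l" and maternal "alpha1-acid glycoprotein (AGP", each to be summarised by its IQR. Infant CRP and AGP are not listed. The adjustment covariates in SAP section 12 contain no inflammation term.

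Protocol 6.11 puts the infant markers in one panel: "Infant anemia, hemoglobin, serum ferritin, transferrin receptor and acute phase proteins such as AGP and CRP", "for all enrolled subjects upon consent from parents". For mothers, "Blood specimen will also be collected from the same 50 randomly selected LWs", which items (a) and (b) of the same section show to be 50 per arm. The table in Protocol 7.3 schedules these samples at day 40-42, before azithromycin, and again at day 56.

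Only Arm C infants receive azithromycin, as a single dose at day 42 (Protocol 6.4 and 6.9). Of this drug, Protocol 1.1.2 says "it plays a vital role in reducing inflammation because of its anti-inflammatory properties". SAP section 2 makes the effect of the interventions on key micronutrient levels in mother and infant a secondary comparison.

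**The concern.** Ferritin is an acute-phase protein. It rises with inflammation whatever the iron stores, so a fixed cut-off misses some iron-deficient participants who are inflamed. The documents do not state this. It is general laboratory knowledge, and they go only as far as calling CRP and AGP acute phase proteins.

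If inflammation is equally common in all arms, the result is a prevalence that is too low. If one arm receives a drug that lowers inflammation, the error differs by arm and randomisation does not remove it. At day 56, about 14 days after a day-42 dose (56 − 42), Arm C infants could have lower ferritin than Arm A or B infants with identical iron stores. A reader could then take the difference as azithromycin worsening iron status.

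**Working it through.** **No figure in the plan to reproduce.** The documents give no expected prevalence, ferritin distribution or power for iron deficiency. What follows is an illustration on assumed inputs.

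**Where the mechanism can act**

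| Sample | Azithromycin given before it? | Consequence of uncorrected ferritin |
|---|---|---|
| Infants, day 40-42 | No, sample precedes the dose | Under-counting only |
| Infants, day 56 | Yes, Arm C only | Possible spurious difference, C vs A and C vs B |
| Mothers, both times | Never dosed | Under-counting only |

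**Model.** Log-ferritin is normal with SD s, true deficiency is P0 in every arm, and inflammation multiplies ferritin by r. Measured deficiency among the inflamed is

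q = Φ(z(P0) − ln(r)/s).

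If inflammation is present in a fraction p of a non-azithromycin arm (A or B) and p_C of Arm C, the spurious Arm C excess is (p − p_C) × (P0 − q). The under-count in an arm with inflammation p is p × (P0 − q).

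**Assumed inputs (none from the documents):** r = 1.3 to 1.6; s = 0.7 to 0.9; p = 30%; p_C = 15%.

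*True deficiency 20-40%*
- Lowest q: P0 = 0.20, r = 1.6, s = 0.7 gives Φ(−0.842 − 0.671) = 0.065.
- Highest q: P0 = 0.40, r = 1.3, s = 0.9 gives Φ(−0.253 − 0.292) = 0.293.
- Smallest excess: P0 = 0.20, r = 1.3, s = 0.9, q = 0.129; 0.15 × (0.200 − 0.129) = 1.1 points.
- Largest excess: P0 = 0.40, r = 1.6, s = 0.7, q = 0.178; 0.15 × (0.400 − 0.178) = 3.3 points.
- Under-count at p = 30%: twice these, about 2.1 to 6.7 points.

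*True deficiency 2-5%*
- Smallest excess: P0 = 0.02, r = 1.3, s = 0.9, q = 0.0095; 0.15 × 0.0105 = 0.2 points.
- Largest excess: P0 = 0.05, r = 1.6, s = 0.7, q = 0.0103; 0.15 × 0.0397 = 0.6 points.

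**Against sampling error.** Take 274 infants per arm, the protocol's number before drop-out inflation. In the 3.3-point case measured deficiency is 33.3% against 36.7%. The standard error is √[(0.333 × 0.667 + 0.367 × 0.633)/274] = 4.1 points, so the shift is 3.34/4.07 = 0.82 standard errors. A nominal two-sided 5% test then rejects with probability Φ(−1.96 + 0.82) + Φ(−1.96 − 0.82) = 0.13. Across the 20-40% range the rejection rate is 6% to 13%; across the 2-5% range it is 5% to 6%.

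**Wider assumptions.** Let P0 = 5-40%, r = 1.3-2.0, s = 0.6-0.9, p = 10-40%, and p_C half of p.
- Excess: from 0.05 × (0.050 − 0.026) = 0.1 points to 0.20 × (0.400 − 0.079) = 6.4 points.
- Under-count in the arm without azithromycin: 0.2 to 12.8 points.
- Rejection rate at 274 per arm: about 5% to 37%.

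In this model a perfect correction brings the spurious difference to zero.

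**The case against.** **Scope.** A reader might infer that every arm comparison of iron status is biased, in mothers as well as infants. The documents do not support that. Mothers never receive azithromycin, the first infant sample precedes the dose, and the documents nowhere claim that the supplement changes systemic inflammation. Under-counting that is similar across arms lowers the prevalence and tends to shrink arm differences; it does not create a false one. This objection stands and limits the point to infants at day 56 in comparisons with Arm C.

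**Premise.** The key assumption is that one dose halves inflammation and that the halving persists at day 56. Nothing in the documents supports that amount. Protocol 1.1.2 does call the drug anti-inflammatory, but after going on to gut flora, immunity and infection it says that the theories are still unproven. This stands: the bias is possible, not shown.

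**Existing safeguard.** Transferrin receptor is reported separately and does not depend on the ferritin cut-off. This stands in part, because the SAP gives no cut-off for it and no rule for combining it with ferritin.

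**Importance.** Iron status has no formal hypothesis, is not among the outcomes named for ANOVA in SAP section 12, and has no row in the SAP's outcome table. The protocol places it under other pre-specified outcomes. In the posited direction the error makes Arm C look worse, so it would not produce a false claim of benefit on iron. All of this stands and keeps the point minor. It does not remove it, because SAP section 2 still makes micronutrient levels a between-arm comparison.

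**Conclusion.** The point holds in a limited form and is a minor improvement. The SAP uses uncorrected ferritin although the markers needed to correct it come from the same samples, and it gives infant CRP and AGP no role. That gap between protocol and SAP stands whatever one assumes about azithromycin.

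The possible spurious excess of deficiency in Arm C is confined to infants at day 56. Its size cannot be known from the documents: about 0.2 to 3 points for true deficiency of 2-40% under the narrower inputs, and 0.1 to 6.4 points under the wider ones. It rests on four assumptions: azithromycin lowers inflammation at day 56, and values for the ferritin ratio, the ferritin spread and true deficiency. At low prevalence it is negligible. A reader might take the upper figures as an expected bias, but the documents give no data to favour them over the lower ones. Elsewhere the supported concern is under-counting in inflamed participants. Length velocity is unaffected.

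**What to change.** In SAP 10.3, before unblinding:

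1. Add infant CRP and AGP at day 40-42 and day 56 to the outcome list.
2. Pre-specify a second definition of iron deficiency, using ferritin corrected by regression on CRP and AGP from the same sample, and report it beside the uncorrected one. State the model and the reference levels of CRP and AGP.
3. Estimate the slopes from the day 40-42 samples pooled over arms, separately for infants and mothers, so that the correction is not fitted to data collected after azithromycin. Applying them at day 56 assumes that the slopes are stable over about two weeks; say so.
4. Use the corrected definition chiefly for the infant day-56 comparisons of Arm C with Arms A and B. For mothers (3 × 50 = 150 sampled), treat it as a descriptive sensitivity analysis.

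This costs a few sentences and a little analysis, with no new sampling. The small downside is that participants without CRP or AGP drop out of the corrected figure; the uncorrected one retains them.
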